a. Diagnosis: SAD and SM are anxiety disorders that develop during the preschool period and appear to share a common developmental diathesis. Children with SAD struggle with social interactions with peers and adults due to elevated anxiety levels; for example, meeting and/or speaking to new people, interacting with peers, being observed by others, or performing in front of others. Symptoms must be present for 6 months.¹⁸ In affected children, the anxiety must be present with peers and not just adults as younger children typically can experience normative anxiety when interacting with adults. As well, in younger children the symptoms may be expressed more behaviourally with crying, tantrums, freezing, or clinging. In SM, significant anxiety prevents children from speaking in social situations. This lack of speech must be present for more than the first month of school¹⁸ as many young children are normatively shy and quiet, especially when placed in new settings with new adults (e.g., new school year with a new teacher and new students). The lack of speech in SM cannot be better accounted for by another psychiatric disorder (e.g. Autism Spectrum Disorder), or communication, learning or language disorders, or be due to a lack of knowledge of the spoken language (e.g., English as a second language).¹⁸

b. Overlap between SAD and SM: In recent years, an increased understanding that debilitating anxiety is the root of a child's lack of speech in SM has led to the conceptualization of SM as a severe developmental variant of SAD. However, it is only since the Diagnostic and Statistical Manual Fifth Edition (DSM-5)¹⁸ was published in 2013 that SM was actually classified as an anxiety disorder. Originally referred to as Elective

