Mutism, due to a belief that children ‘stubbornly’ refused to speak, it was only with growing understanding that anxiety drove the mutism that the disorder was renamed Selective Mutism. Evidence for the common diathesis for the two disorders comes from the high co-morbidity between SAD and SM, with studies showing from greater than 50%¹⁹⁻²¹ to greater than 80% of children with SM also meeting criteria for SAD.^{22,23} Further, the presence of SAD symptoms in older children predicts SM symptom severity.²¹ Although clinicians rate older children (5.4 to 15 years) with SM as having higher levels of SAD compared to children with only SAD, these children do not rate themselves as more socially anxious on self-reports, compared to children with only SAD.²⁴⁻²⁶ In other words, unlike other anxious children, children with SM do not recognize that they are anxious in social situations, which could be a factor contributing to the well-known fact that treating children with SM is particularly difficult.

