Study Design: This study utilizes a repeated measures, longitudinal, randomized controlled trial design to compare the efficacy of two interventions in the treatment of children aged 4 to 7 years with SM and/or SAD. Participants are randomized into either the (1) “*Taming Sneaky Fears for SAD and/or SM*” parent and child group CBT treatment, or (2) the “Parent Psycho-education and Child Socialization” comparison program. Both programs run for 10 consecutive weeks (plus one additional introduction week). To control for the nonspecific factors associated with treatment, such as the support, attention and expectation of improvement, parents and children in both treatment protocols receive comparable levels of attention from therapists (i.e., same duration of group sessions and total number of sessions with a therapist) and comparable opportunities for socialization (e.g., for the children: invitation to discuss how the previous week went, snack time, story time; for the parents: discussion of specific topics at each session). However, parents and children in the comparison group are not taught CBT strategies.

Participants:

Inclusion Criteria: 4 to 7 year old children referred for psychiatric assessment of SM and/or SAD who meet diagnostic criteria for SM and/or SAD as a primary diagnosis, as determined by 1 of the 4 psychiatrists at the 2 sites where the study is conducted. Presence of other anxiety disorders/symptoms is not an exclusion criterion as long as the main concern is SAD and/or SM.

Exclusion Criteria: Presence of autism spectrum disorder, brain injury, or significant developmental delays (based on medical history and clinical assessment). Children and parents not fluent in English.

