Pre-treatment Research Assessment (Time 1 [T1]) takes place ~2 weeks prior to group-treatment start. Parent questionnaires are reviewed by a Clinical Research Project Coordinator (CRPC) to ensure completion. The CRPC administers the ADIS-P with the parent and then completes the '10 Steps to Talking' with the child in the presence of the parent (video-recorded). The only speech and language assessment completed as part of the study is conducted (and video-recorded) at this T1 visit. Upon completion of the T1 visit, the CRPC **randomly assigns** each eligible child and parent to either the (1) "*Taming Sneaky Fears for SAD and/or SM*" parent and child group CBT program or (2) the "*Parent Psycho-education and Child Socialization*" group program, and informs them of group assignment. The online software *Sealed Envelope*TM (<https://www.sealedenvelope.com/>) is used to randomize. This program is commonly used by hospital research studies because it uses computer-generated sequences to allocate participants to each group. Allocation of participants uses sealed, opaque envelopes and remains concealed until study completion. The CRPC and lead child group and parent group therapists ([name]) are not blinded, however, the clinicians completing the post-intervention (T2) and 6-month follow up (T3) assessments are blind to treatment type, previous ratings on all measures, and time of assessment.

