To address Hypothesis 1, we will use a two-sided Chi-Square test with continuity correction to compare the difference between the two 2 groups in the proportion of children who lost diagnoses post-treatment (T2) and 6 months post-treatment (T3).

To test Hypothesis 2, we will use a repeated measures regression model on the ADIS-CSR and compare the two 2 treatment groups from pre-treatment (T1) to 6-month post treatment (T3). An interaction term between time and group will be introduced in the model in order to explore possible differences at different time points between the two groups. The assumptions of the model will be verified using residual analysis and, if necessary, transformations will be used in order to obtain a valid model. This repeated measures regression model will be used for Hypotheses 3 and 4 to assess child global functioning using CGAS and parent and teacher reports of child symptoms on SMQ, SASC-P/T and SSQ.

To examine Hypothesis 5, a logistic regression analysis will be employed. This will allow for the examination of the strength of multiple predictors on the likelihood that a child will lose an anxiety disorder diagnosis 6 months post-intervention (T3). The predictor factors that will be included in this model include group intervention (“*Taming Sneaky Fears for SAD and/or SM*” or “Parent Psycho-education and Child Socialization”), within-the-child factors (child’s age, sex, BI, and speech-language difficulties), parent factors (family history of SAD or SM), and environmental factors (family stress, immigration status). All the significant factors will be put into the model and non-significant predictors will be excluded. The model will control for age and sex of the child.

ORIGINALITY AND SIGNIFICANCE/RELEVANCE: This is the first RCT to assess the efficacy of “*Taming Sneaky Fears for SAD and/or SM*”, a group CBT treatment approach to treat 4 to 7 year old children with SM and/or SAD, which are anxiety disorders affecting as many as 36,340 children under age 14 in Ontario. The present study addresses methodological shortcomings of previous studies and builds on OMHF-funded previous work while addressing a significant clinical problem for which little convincing evidence for treatment efficacy exists. The present study represents an innovative treatment method that is brief, CBT-based, and group-focused.

Timeline of the Study:

REFERENCES

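### The model of treatment outcome (Hypothesis 5) omits whether the child entered with selective mutism, and no result by entry diagnosis is planned

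*Combined protocol and SAP*

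**What the plan says.** - **Entry (Methods, Inclusion Criteria).** The trial takes 4 to 7 year olds "who meet diagnostic criteria for SM and/or SAD as a primary diagnosis". Children with SAD only, SM only and both are pooled.
- **Difference between the disorders (Background, item b).** The protocol describes the "conceptualization of SM as a severe developmental variant of SAD" and refers to the "well-known fact that treating children with SM is particularly difficult".
- **Overlap (same item).** It also reports high comorbidity, from over half "to greater than 80% of children with SM also meeting criteria for SAD", and uses this to argue for a common origin.
- **Randomisation (Pre-treatment Research Assessment).** The ADIS-P is given at T1, and allocation follows that visit. The software "uses computer-generated sequences to allocate participants to each group". No stratification factor is named.
- **Hypothesis 1 (Statistical Analysis and Data Analyses Plan).** For loss of diagnosis, "we will use a two-sided Chi-Square test with continuity correction to compare the difference between the two 2 groups". There is no stratum or covariate.
- **Hypothesis 5 (same section, and Research Questions).** The logistic model at T3 takes treatment group, age, "sex, BI, and speech-language difficulties), parent factors (family history of SAD or SM", family stress and immigration status. Non-significant predictors are dropped; age and sex are controlled for. The family history item concerns relatives, so the child's own diagnosis is on neither list.

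**The concern.** The third objective is to find what predicts treatment outcome. The model for it leaves out the one child characteristic that the protocol itself links to treatment difficulty, but keeps variables that may partly stand in for it. Background item c names speech and language difficulties, and family immigration, as possible risk factors for SM. The speech-language rating also has a category for children who could not be tested for lack of compliance (Measures, section E), and a child who does not speak to unfamiliar adults could plausibly fall there because of SM. If such a variable is retained as significant, nobody could say whether it reflects language, immigration or SM.

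The second cost is interpretive. The Background says that no treatment study has focused on young children with SAD and that only a few have focused on SM. The planning rate of 10/24 was already pooled over the two disorders. As written, this trial would add another pooled figure.

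**Working it through.** **1. The plan's own figure.** Inputs from Sample Size Calculation: 42% v 10% loss of diagnosis, two-sided 0.05, continuity-corrected chi-square. The Fleiss formula gives 35 per arm with 81.1% power, and 70/0.80 = 87.5, so 88 recruited. The stated figures reproduce. Exact power of the corrected test at 35 + 35 is 83.2%, the reference value below.

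**2. Is entry diagnosis covered elsewhere?** The listed predictors, set against the protocol's account of SM:

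| Predictor | Link to SM in the protocol |
|---|---|
| Speech-language difficulties | possible SM risk factor |
| Immigration status | possible SM risk factor |
| Behavioural inhibition | risk factor for both disorders |
| Family history of SAD or SM | relatives, not the child |
| Age, sex, family stress | none stated |

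None is the child's diagnosis; two overlap with SM specifically.

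**3. Events available to Hypothesis 5.**
- At the planned post-treatment rates: 35 × 0.42 + 35 × 0.10 = 14.7 + 3.5 = 18.2 losses. With eight listed predictors that is 18.2/8 = 2.3 events per predictor; with nine, 18.2/9 = 2.0.
- Hypothesis 5 is assessed at T3. The earlier study's 6-month rate was 67%. The documents give no T3 comparison rate; if 10% is assumed, 35 × 0.67 + 35 × 0.10 = 27 losses, or 3.4 per predictor falling to 3.0.

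**4. Precision by stratum.** This assumes 42% v 10% within the stratum. SE = √[(0.42 × 0.58 + 0.10 × 0.90)/n] = √(0.3336/n).
- 50% SM share, n = 17.5 per arm: SE 0.138, 95% interval about ±27 points.
- 80% SM share, SAD-only stratum, n = 7 per arm: SE 0.218, about ±43 points.

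**5. What omission costs Hypothesis 1.** The documents give neither the SM share nor loss rates by diagnosis, so these are assumptions.
- Chance of an SM imbalance of 20 points or more, in either direction, under simple randomisation with 35 per arm: 12% at a 50% SM share, 10% at 65%, 5% at 80%.
- Effect of a 20-point imbalance, with loss rates SAD-only/SM of 57/27 (CBT) and 15/5 (comparison). With 60% SM in the CBT arm and 40% in the other: CBT 0.4 × 57 + 0.6 × 27 = 39%; comparison 0.6 × 15 + 0.4 × 5 = 11%. The difference is 28 instead of 32, a shift of 4 points.
- Simulated power, 50% SM share, overall rates held at 42% v 10%, continuity-corrected tests:

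| SM/SAD gap in CBT arm | Unstratified | Stratified test only | Stratified randomisation and test |
|---|---|---|---|
| 0 | 83% | 82% | 83% |
| 20 | 83% | 83% | 84% |
| 30 | 83% | 84% | 85% |
| 40 | 83% | 86% | 87% |

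At an 80% SM share with a 20-point gap there is no gain. Type I error of the unstratified corrected test is about 3%.

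**The case against.** The best counter-argument is that the prognostic premise is thin. The remark on difficulty is made in passing and carries no loss rates. The SM figures that the Background does give are 2/5 (40%) in a small CBT case series and 67% of completers in a 24-week trial. The pooled figures from the earlier study are 42% post-treatment and 67% at 6 months. The samples are small and the programmes differ, but nothing there shows SM doing worse. The protocol also argues for a common origin and high comorbidity, which is its reason for pooling. This stands as a limit on weight. It does not justify omission from Hypothesis 5, whose purpose is to find out which factors matter.

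The model is also already crowded for its number of events, and stratum results will be imprecise. Both points stand, and they are why the stratum results should be labelled descriptive.

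A reader might go further and infer that the primary comparison is biased, that the trial is underpowered, or that the randomisation must be stratified. The documents do not support this. Randomisation keeps Hypothesis 1 valid, imbalance is chance variation, and the gain in power is small or absent. The protocol is silent on stratification; it does not say that none is used. Nor does it follow that behavioural inhibition would stand in for SM, since the protocol treats it as a risk factor for both disorders.

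**Conclusion.** The gap is real but confined to Hypothesis 5 and to reporting. Entry diagnosis is missing from the outcome model, so an SM effect could not be told apart from a speech-language or immigration effect, and only a pooled result would be available. This conclusion rests on the text and needs no assumed rates.

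For Hypothesis 1 the consequence is minor: about -1 to +4 points of power over assumed gaps of 0 to 40 points, and a shift of roughly 4 points in the arm difference from a 20-point imbalance under the assumed 57/27 v 15/5 rates. An imbalance at least that large arises in about 5 to 12% of trials at SM shares of 80 to 50%, counting both directions. The planned test and sample size can stay.

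**What to change.** - **Hypothesis 5 (Research Questions, and Statistical Analysis and Data Analyses Plan).** Add entry diagnosis, coded SM present or absent on the T1 ADIS-P. Keep it in the model regardless of significance, beside age and sex. This coding keeps children with both disorders together with SM-only children, so it tolerates comorbidity.
- **Reporting.** Give loss of diagnosis by arm within each stratum at T2 and T3, with confidence intervals, labelled descriptive.
- **Optional.** Run a continuity-corrected Mantel-Haenszel test over the same stratum as a sensitivity analysis for Hypothesis 1; the planned chi-square remains primary.
- **Optional.** Stratify the randomisation, but only for cohorts not yet randomised. The document is dated February 2016, and three of the five cohorts were scheduled to start in September to November 2015. The coordinator who gives the T1 interview also randomises, so small blocks within strata could make allocations easier to predict.

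The cost is a few lines of analysis text, with no new data, visits or participants. The price is one more model term on about 18 to 27 events and wide stratum intervals. The change should be recorded before outcome data are examined by arm.

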Sample Size Calculation is based on data from our previous OMHF study, showing that 42% of children in the “*Taming Sneaky Fears*” program lost their primary diagnosis of SAD and/or SM post-intervention vs. none of the children in the comparison group (using the ADIS-P). In the present study, we conservatively estimate that 10% of children will lose their SAD and/or SM diagnosis in the comparison group. Hence using this difference of 32% (42% - 10%), a sample size of 69 (to round up, 35 subjects per treatment protocol) would achieve a power of 81% to detect a difference of 32% between treatment programs using a two-sided Chi-squared test with continuity correction with a significance level set at 0.05.⁶⁵ Further, a total of 15/77 children (19%) did not complete the full protocol in the original OMHF study, so we anticipate a 20% (n=18) dropout rate over the course of this study. As a result, 88 participants need to be recruited to ensure a final sample size of 70. In order to obtain a sample size of 88

participants over two years, 2 sites are necessary.

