Sites: The 2 sites chosen for recruitment are both tertiary care treatment centers affiliated with the University of Toronto: The Hospital for Sick Children (HSC) and Toronto East General Hospital (TEGH). Both sites house pediatric anxiety disorders clinics and serve large urban/suburban populations. TEGH and HSC are approximately 5 km apart, accept referrals for assessment and treatment from anywhere within the greater Toronto area (GTA), and are easily accessible for families living within the GTA. Respectively 50 and 25 children between the ages of 4 and 7 with SAD and/or SM are referred to HSC and TEGH every year, yielding a total of 75 children assessed per year at the two sites. It is our experience that the majority (approximately 90%) of children attending assessments in our anxiety clinic for either SAD or SM meet criteria for one or both of these diagnoses, thus suggesting that 70 children (.90 x 75 total = 67 eligible patients) will be eligible for study participation per year from the 2 sites. Further, given the academic affiliation of our sites, families attending our clinics are receptive to participation in research studies and conservatively, we find that close to 75 to 80% of families approached are interested and willing to participate in research studies. As a result, we anticipate that 50 to 53 families (.75 x 67 to .80 x 67) from the 2 sites are likely to participate in the study each year. Therefore, it is both feasible and realistic to not only recruit the necessary 88 children, but also to retain the necessary minimum sample size of 70 children over the 2-year study, even when considering attrition over the longer-term follow-up.

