Recruitment: Children referred for an assessment of SAD and/or SM at either site are assessed by 1 of the 4 child psychiatrists, who obtains information about presenting problem, its impact on the child's functioning at school, home and with peers, and developmental, medical and family history. Eligible, interested children and families meet with a Clinical Research Project Coordinator (coordinator) who describes the study immediately post-assessment at either HSC or TEGH (depending on site where child was assessed). The coordinator obtains informed consent from parent(s) and assent from child, gives pre-treatment questionnaires to the parent(s), and schedules the first research assessment visit (Time 1) at HSC within 2 to 3 weeks of assessment and start of treatment group. Children and families not eligible for the study or who decline to participate are treated or referred for appropriate treatment as usually done in each clinic.

Measures: A demographic questionnaire (child's age and gender, parent's name, family composition, family history of SAD or SM, and immigration status) is completed by the parent at the start of the study.

A. Clinician Rated Measures:

- 1) The Anxiety Disorders Interview Schedule for DSM-IV, Parent Version (ADIS-P)⁵⁹ is used to assess SAD and/or SM. The ADIS-P has good reliability,⁶⁶ is sensitive to treatment effects in child anxiety studies,^{66,67} and has been used in a number of studies on preschoolers^{45,46,48} and SM treatment.⁵⁸ Clinical Severity Rating (ADIS-CSR) uses a 0 to 8 scale to measure clinical severity of diagnosis; a CSR of ≥ 4 indicates clinically significant symptoms and presence of an anxiety disorder. A trained independent clinician blinded to treatment type and time of assessment completes the CSR.
- 2) The Children's Global Assessment Scale (CGAS)⁶¹ assesses adaptive functioning during the previous month for children aged 4-16 years. It has high inter-rater and test-retest reliability. A trained independent clinician blinded to treatment type and time of assessment completes the CGAS.

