- 4) The Strengths and Weaknesses of ADHD and Normal Behaviour (SWAN) rating scale is a 30-item parent-report that measures a child's ability to attend and control impulsive behaviour (e.g. oppositional behaviours). Items are rated on a 7-point scale from "far below" to "far above". This instrument has been demonstrated to be both reliable and valid.^{77,78}

C. Teacher Report of Child Symptoms:

- 1) The School Speech Questionnaire (SSQ)⁶⁴ is a 4-point rating scale of frequency of speaking behaviours at school, ranging from 0 (never) to 3 (always), that is sensitive to teacher-noted symptom improvement.^{59,60} A lower score indicates higher severity and impairment. Internal consistency is satisfactory.⁵⁹
- 2) The Social Anxiety Scale of Children-Revised Teacher version (SASC-T; see above)⁶³ is adapted by the Bergman group to allow teachers to quantify social anxiety symptoms within the school setting.

D. Parent Measures:

- 1) The Depression Anxiety Stress Scales short version (DASS-21)⁷² is a 21-item self-report of anxiety and depression in adults, using a 4-point scale ranging from 0 ('did not apply to me at all over the last week') to 3 ('most of the time over the past week'). It has excellent psychometric properties⁷³ including adequate convergent and divergent validity with clinical assessment and the Beck Depression Inventory.⁷⁴ Only the anxiety and stress subscales are used in the present study.
- 2) Parenting Stress Index–Short Form (PSI-SF)⁷⁵ has 36 items, measures the magnitude of stress in the parent–child relationship, has good test-retest reliability and internal consistency,⁷⁶ and is used as a measure of stress in the present study. Raw scores of ≥ 90 indicate clinically significant levels of stress.

E. Speech and Language Testing: is completed by a speech language pathologist at the pre-treatment assessment only. Children's speech and language skills are categorized as 1) age appropriate; 2) suspected delay/disorder; 3) confirmed delay/disorder; 4) unable to determine due to lack of compliance in testing, and used as a within-the-child factor.

Research Protocol: The full research protocol takes 9 months for each child and parent to complete and includes a total of 3 research visits (T1, T2, T3) and 11 treatment visits to the HSC Department of Psychiatry. Time between assessment and first research visit is approximately 2-3 weeks.

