Implementation of Treatment Protocols: Both group treatment protocols run concurrently, but on different days. A total of 5 “*Taming Sneaky Fears*” and 5 “*Parent Psycho-education and Child Socialization*” groups need to run over the course of the 2-year study with 8 - 9 children per group (total of 40 - 45 children per treatment arm over study period). Groups run weekly for 1 hour for nearly 3 months (10 + 1 sessions) starting in September 2015, October 2015, November 2015, March 2016, and April 2016. As the final treatment groups for the study are completed by mid-July 2016, the final 6-month follow-up takes place in mid-January 2017, prior to the end of the study (see Time line of Study p. 10). Regardless of the treatment program, the first treatment visit is for parents only at which time parents are introduced to the therapists and other parents in the group and provided a copy of the “*Parent Manual*” relevant for each group (either the Parent Manual for “*Taming Sneaky Fears for SAD and SM*” or the one for “*Parent Psycho-education and Child Socialization*” that includes handouts provided as part of the “*Improving Parent-Child Relationship*” series of videotapes).

In both treatment protocols, parents and children attend weekly, 1-hour group sessions for 10 consecutive weeks at HSC. In order for the 2 treatments to be comparable, each child group follows the same format, i.e., starts with a ‘review of the week’, followed by a story then craft activity and ends with a snack. At the end of each session, a child therapist drops into the parent group to inform parents about strategies and activities taught to children that day (typically, a 30-second general summary). At the mid-point of both group treatments, a child therapist meets with parent(s) individually to discuss their child’s progress. Therefore, children in both treatments receive equal opportunities for interaction with therapists and socialization with peers with the only difference between groups being that children in the “*Taming Sneaky Fears for SAD and/or SM*” group receive CBT while the children in the comparison group do not. Similarly, both parent groups start with a review of homework, then new information is provided and finally, homework is assigned; with the main difference between groups being that in “*Taming Sneaky Fears for SAD and/or SM*” parents receive CBT.

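### The forecast of 88 recruits uses two full years of accrual, but the plan's calendar leaves about 15 months if the study spans 24 (about 60 to 69 families at the stated rate)

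*Combined protocol and SAP*

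**What the plan says.** The Sample Size Calculation section sets the target: "88 participants need to be recruited to ensure a final sample size of 70". It adds that two sites are needed to reach this number, in the words "participants over two years, 2 sites are necessary".

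The Sites section supplies the rate. Referrals are put at 50 and 25 a year at the two hospitals, "yielding a total of 75 children assessed per year at the two sites". About 90% are expected to meet criteria, which the section gives both as a calculated 67 and as a rounded 70 a year. With 75 to 80% uptake, "we anticipate that 50 to 53 families (.75 x 67 to .80 x 67) from the 2 sites are likely to participate" each year. From this the section concludes that it is realistic to recruit 88 and to "retain the necessary minimum sample size of 70 children over the 2-year study", with attrition over the longer follow-up taken into account.

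Two other sections set the calendar. Research Protocol states: "The full research protocol takes 9 months for each child and parent to complete". Implementation of Treatment Protocols has five groups per arm within the two-year study, with 8 to 9 children each, "starting in September 2015, October 2015, November 2015, March 2016, and April 2016". The last groups finish by mid-July 2016, and the last 6-month follow-up is in mid-January 2017, before the study ends.

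**The concern.** Two years at 50 to 53 families gives 100 to 106, which comfortably covers 88. That comparison works only if nearly the whole two years is open for enrolment. The last children must be enrolled by the April 2016 groups, and they then occupy about 9 months of the same period. The Sites section allows for children lost during follow-up but does not subtract the time that follow-up takes.

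If accrual runs at the stated rate within a 24-month study, fewer children are enrolled and analysed than planned. The primary comparison of lost diagnoses at T2 (post-treatment) may then have less power than stated. The forecast is what connects the powered sample of 70 to a number the clinics can supply, so it should agree with the calendar.

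**Working it through.** **Inputs.** Sample Size Calculation: 42% versus 10%, two-sided 0.05, continuity-corrected chi-square, 70 completers, 20% loss, 88 recruits. Sites: 75 referrals a year, 67 (rounded to 70) eligible, 75 to 80% uptake. Research Protocol: 9 months per family. Implementation of Treatment Protocols: last start April 2016, last follow-up mid-January 2017. Assumption: the two-year study spans 24 months.

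**1. The plan's own figures reproduce.**
- With d = 0.32, the corrected sample size is 35 per arm.
- Power at n per arm uses n' = n − 2/d + 1/(n d²), entered in the uncorrected formula. At n = 35, n' = 29.03 and power is 0.811, the stated 81%.
- 70/0.80 = 87.5, rounded up to 88.
- 0.75 × 67 = 50.25 and 0.80 × 67 = 53.6 families a year.

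**2. Accrual window.** The study ends no earlier than mid-January 2017, so a 24-month study opens no earlier than about mid-January 2015. From then to April 2016 is 14.5 months (1 April) to 15.5 months (30 April). As a cross-check, 24 − 9 = 15.

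**3. Yield in that window.**
- Low: 14.5 × 50/12 = 60.4.
- Middle: 15 × 53.6/12 = 67.0.
- High: 15.5 × 53.6/12 = 69.2.
- Most generous, with the rounded 70 eligible at 80% (56 a year): 15.5 × 56/12 = 72.3.

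**4. Time and rate needed for 88.**
- At 50 a year: 88/50 × 12 = 21.1 months. At 53.6: 19.7. At 56: 18.9.
- To fit 15 months: 88/15 × 12 = 70.4 families a year, more than every eligible child on either figure (67 or 70).

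**5. Children left after 20% loss.** 60 × 0.8 = 48; 69 × 0.8 = 55; 72 × 0.8 = 58, against 70.

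**6. Continuity-corrected power at T2, 42% versus 10%.**

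| Case | Children analysed | Per arm | Power |
|---|---|---|---|
| All loss before T2, low | 48 | 24 | 0.60 |
| All loss before T2, most generous | 58 | 29 | 0.71 |
| No loss before T2, low | 60 | 30 | 0.73 |
| No loss before T2, stated rate, high | 69 | 34.5 | 0.80 |
| No loss before T2, most generous | 72 | 36 | 0.82 |
| As planned | 70 | 35 | 0.81 |

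No power is computed for the 6-month follow-up, because the plan gives no comparison-arm rate for that time.

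**The case against.** The strongest reply is that the deciding date is not visible. Implementation of Treatment Protocols refers to a timeline whose content did not survive in the copy reviewed, and that loss is not a fault in the plan. The text never ties the two years to calendar dates, and the Sample Size Calculation section could mean two years of recruitment alone. This stands as a condition on the finding, but it does not remove the conflict. At the stated rate, 88 by mid-April 2016 requires accrual from about July to August 2014 (September 2014 at 56 a year). That is about 28 to 30 months before mid-January 2017, while the Sites section places retention through follow-up inside the two-year study.

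Two supply arguments are weaker. The 80 to 90 group places are capacity, not a source of families. The background section reports rising referrals, but the Sites section plans on a fixed 75 a year.

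It is also fair to say that the effect on power may be small. The 20% loss is stated for the whole study, so part of it may fall after T2. With no earlier loss, power at T2 lies between about 73% and the stated level. That stands.

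A reader might infer a much shorter window, of about 8 to 9 months. The Recruitment section says that the coordinator "schedules the first research assessment visit (Time 1) at HSC within 2 to 3 weeks of assessment and start of treatment group", and the first groups start in September 2015. The documents do not support that reading. No groups start between November 2015 and March 2016, so counting those months already assumes that children wait for a group. Nothing says that children assessed before September 2015 could not wait as well.

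**Conclusion.** The accrual forecast and the calendar do not agree if the two-year study means 24 months. On that assumption, and at the rate in the Sites section, about 60 to 69 families can be enrolled (up to about 72 with the rounded eligibility figure), a shortfall of roughly 16 to 28 against 88. The loss of power at T2 is uncertain: substantial if dropout comes early, negligible if it comes late and accrual is at the top of the range.

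A reader might infer that the sample size calculation is wrong or that the result would be biased. Neither follows. The 81% is correct for 70 completers, the requirement of 70 is unchanged, and a smaller sample biases neither the estimate nor the test. The plan also does not say that recruitment will close short of target. This is an inconsistency in a feasibility argument, of low severity.

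**What to change.** Reconcile the Sample Size Calculation and Sites sections with Research Protocol and Implementation of Treatment Protocols. Count only the months from the study's opening date to the last group start, then restate the expected numbers enrolled and analysed with the matching power, saying how much of the 20% loss is expected before T2. If an earlier opening, a pool of children already assessed, or higher referrals supports 88, state that in place of the two-year accrual argument.

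The cost is a few sentences and possibly a less favourable stated figure. Design, endpoint and analysis do not change.
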